2.2 Study rationale

The optimal treatment for DSA in lung transplant recipients remains unclear. In a recent study, 65 lung transplant recipients who developed DSA were treated preemptively before the development of BOS with either IVIG alone or IVIG/rituximab.¹³ On follow-up evaluation, persistence of DSA despite therapy was associated with increased BOS (Figure 3B). However, recipients treated with IVIG alone had persistence of DSA comparable to those treated with IVIG/rituximab (35% vs.38%, respectively). Thus, while there was no untreated control group, these data suggest that the addition of rituximab therapy did not enhance DSA clearance and had no significant effect on freedom from BOS (Figure 3A) compared to IVIG alone. These data indicate that either IVIG alone or IVIG/rituximab therapy results in substantial persistence of DSA in lung transplant recipients (35%), and is associated with significantly increased progression to BOS.

[figure not shown]

Figure 3. Freedom from BOS in lung transplant recipients with DSA treated with IVIG vs. IVIG/rituximab and in patients who cleared vs. persisted DSA.

Since rituximab appears to add little to conventional therapy, proteasome inhibition with bortezomib alone and in combination with conventional therapy was investigated in 6 renal transplant recipients. Bortezomib-based therapy effectively treated 6 patients with refractory combined AMR/ACR and stably reduced DSA by at least 50% (figure 4, next page). Moreover, a single cycle of Bortezomib alone was as effective as Bortezomib combined with PLEX and IVIG or rituximab in reducing de novo DSA. MFI< 1000) which lasted >2 years in 3/7.41 Patients with stable CR, had a lower serum CR at 14 months than those with DSA relapse –adding credence to the notion that successful treatment of DSA may alter outcome. Importantly proteasome inhibitors were well tolerated, and neither overall IgG nor IgG levels for childhood immunizations were changed. The relatively specific loss of DSA after proteasome inhibitor therapy may relate to their predominant effect on the most active antibody responses, with residual DSA binding to the allograft. Interestingly, recent evidence in vitro indicates that proteasome inhibitors induce B cell apoptosis in addition to the effects on plasma cells and therefore, may impact and expand cell populations targeted by anti-CD20 based therapies. Is

[figure not shown]

3. OBJECTIVES

3.1 Objectives

Short-term outcomes after lung transplantation are improved; however, long-term outcomes remain poor and this is a major challenge for the field. Progressive allograft dysfunction due to

the clinical diagnosis of bronchiolitis obliterans syndrome, or chronic rejection, limits both patient survival and quality of life. The impact of donor-specific anti HLA-antibodies (DSA) and AMR on the early development and progression of BOS have been well-described.^{3,13,22} In addition to these data, our preliminary data show a dramatic reduction in lung function in the presence of DSA, accelerated diagnosis of phenotypically more advanced BOS, and early mortality. At present, targeting this pathway represents a viable approach to impact these key risk factors, DSA and AMR, and decrease expression of chronic rejection, graft loss, and patient death. Additionally, major gaps in our knowledge of the antibody-mediated phenotype of BOS exist. While early evidence of clinical benefit appears to exist in our preliminary data, this needs to be validated with larger patient numbers. Moreover, the underlying mechanisms of potential benefit remain to be elucidated.

Conventional therapy for this problem, including plasma exchange and intravenous immunoglobulins, are limited and targeted at removal of circulating antibody; not at the antibody-producing apparatus, the plasma cell. Thus, our hypothesis is that the combination of conventional therapy with plasma-cell targeted therapy using the proteasome-inhibitor carfilzomib in symptomatic lung transplant recipients with AMR will improve/stabilize allograft function and result in depletion of the immunodominant DSA. In this proposal, we will conduct a pilot phase II open label observational trial in lung transplant recipients to test whether addition of carfilzomib to conventional therapy improves short-term outcomes after the diagnosis of antibody-mediated rejection, and to identify the cellular mechanisms that support these clinical benefits. Clinical and immune phenotyping of study subjects will advance our understanding of anticipated therapeutic responses. Specifically, cellular mechanistic studies to detect immune system changes that will enable us to phenotype LTRs with AMR and determine or predict risk and outcomes, such as BOS. Patients who have met the clinical diagnosis of AMR requiring therapy will be targeted for enrollment in the study and treated with the open-label carfilzomib-based combination protocol.

To execute this study, we have established the Combination Therapy with the Proteasome Inhibitor Carfilzomib for the Antibody-Mediated Rejection Diagnosis in Lung Transplantation (PICARD-Lung) Trial Study Group. This clinical trial will be executed at the University of Pittsburgh Medical Center leveraging the expertise and prowess of one of the highest-volume clinical lung transplant services worldwide, the [name] immunology lab, and the [name] immunohistochemistry and histocompatibility labs.

- 1: To test the hypothesis in a prospective interventional clinical trial that addition of carfilzomib to conventional therapy will result in depletion of the immunodominant DSA. In this trial, lung transplant recipients will be treated with the carfilzomib-based combination protocol and screened with Luminex single antigen bead testing to identify DSA burden by IgG and functional status by C1q before and after treatment.
- 2: To test the hypothesis in a prospective interventional clinical trial that addition of carfilzomib to conventional therapy will result in improved or stabilized allograft function. In this trial, lung transplant recipients will be treated with the carfilzomib-based combination protocol and screened with pulmonary function testing to identify whether forced expiratory volume in 1 second returns to pre-AMR diagnosis level.
- 3: To test the hypothesis that lung transplant recipients with AMR have effector B cell/plasma cell populations that can be identified and characterized, and that carfilzomib alters these immune mechanisms. In this trial, we will determine the immunologic phenotype

of these patients and describe functional immune system changes in memory and effector cells, plasma cells, and respective pathologic and immunohistochemical correlates relevant to AMR.

The PICARD-Lung investigators and the study center are highly experienced clinical and translational investigations in lung transplantation. Successful completion of these specific aims will establish the safety and efficacy of combination therapy with carfilzomib/PLEx/IVIG for AMR after lung transplantation and elucidate important clinical and immunologic phenotypes and mechanisms associated with these outcomes. Thus, the results of this trial will advance treatment efforts for AMR, which are desperately needed, as well as provide important insights into the link between AMR and BOS, the latter of which significantly limits long-term outcomes in lung transplant recipients. Lastly, we fully anticipate this study will lay the foundation for future clinical and basic investigation, perhaps at the multi-center level, to further delineate the role and immune effects of carfilzomib in the treatment of AMR and the prevention of BOS.

4 STUDY DESIGN

Phase II, prospective, open-label, single-arm active treatment, single center pilot clinical trial of the addition of carfilzomib to conventional therapy for AMR after lung transplantation.

Study site: University of Pittsburgh Medical Center, Pittsburgh PA USA

Conventional therapy for AMR: Therapeutic plasma exchange (PLEX) 1.5 plasma volumes replaced with 5% albumin or fresh frozen plasma for 8 sessions every-other day. Total intravenous immunoglobulins (IVIG) 100 mg/kg IV after each PLEX with the exception of the final PLEX where IVIG 500 mg/kg will be given. On day 16, if the IgG level is below 700 mg/dL, an additional dose of IVIG 500 mg/kg will be administered. If the IgG result is found to be 700ml/dL or higher, the IVIG 500mg/kg dose will not be administered. Premedications will be given for IVIG as follows: acetaminophen 650 mg PO and diphenhydramine 25 mg PO both at least 30 minutes prior to and not more than 6 hours before IVIG, unless otherwise directed on the part of one of the investigators if believed to be in the best interests of patient care. On days where IVIG and CFZ are given together, only one set of premedications will be administered. Conventional therapy requires an inpatient hospital stay. Patients will receive a tunneled PLEX catheter and peripherally inserted central catheter (PICC) inserted by interventional radiology in the routine clinical care of these patients prior to receiving any conventional or carfilzomib therapy.

Carfilzomib dosing schedule: Carfilzomib will be administered on the multiple myeloma schedule consisting of 20 mg/m² on days 1, 2, 8, 9, 15, and 16 to constitute one therapeutic cycle. On PLEX/IVIG days, carfilzomib will be given in between PLEX and IVIG to avoid inadvertent blockade of the Fcγ receptor. Carfilzomib will be delivered via central access IV over 30 minutes (+15 minutes); slowed to 60 minutes (+15 minutes) if infusion reactions occur. Carfilzomib will be diluted in a total of 80 mL dextrose 5% water (D5W) for administration. Premedications for carfilzomib administration will be given as follows: acetaminophen 650 mg PO, diphenhydramine 25 mg PO, ondansetron 4 mg PO, prednisone 40 mg PO or methylprednisolone 40 mg IV, all at least 30 minutes prior to and not more than 6 hours before carfilzomib, unless otherwise directed on the part of one of the investigators if believed to be in the best interests of patient care. Preinfusion hydration with a one-time bolus of 250 mL 0.9% sodium chloride will be given at least 30 minutes prior to and not more than 6 hours before carfilzomib to minimize the nephrotoxic AE. Postinfusion hydration with a one-time bolus of 250 mL 0.9% sodium chloride may be given immediately after carfilzomib to minimize the nephrotoxic AE

4.1 Rationale

Carfilzomib is marketed for multiple myeloma and this IST represents an off label use of carfilzomib; thus, the criteria for phase II designation have been met. This prospective, open-label, single-arm active treatment trial will establish the rate of response to carfilzomib (in addition to conventional therapy) for AMR after lung transplantation. This information will be necessary for use in planning further larger dual-arm placebo or active therapy controlled clinical trials. This trial will enroll 30 patients at the University of Pittsburgh Medical Center. The volume of lung transplants performed and the rate of diagnosis of AMR at UPMC will allow for adequate enrollment of study patients within the 3-year study period.

The dosing strategy of carfilzomib will follow that of the multiple myeloma schedule as described below in section 5.3. This dosing strategy has been well-studied in patients with myeloma (see trial designations below) and has proven to result in an acceptable AE profile for the patients with AMR after lung transplantation. In addition, our preliminary off label experiences with this dosing strategy have yielded an acceptable AE profile in lung transplant recipients with AMR.

Trial designations:

Carfilzomib has been evaluated in 2 completed Phase 1 studies (PX-171-001 and PX-171-002), 5 completed Phase 1b/2 studies (PX-171-003, PX-171-004, PX-171-005, PX-171-006, and PX-171-008), and in 1 completed, Phase 2, expanded-access study (Study 2011-002, Carfilzomib Multiple Myeloma Expanded Access Protocol [C-MAP]) that was co-sponsored by Amgen and the Multiple Myeloma Research Foundation.

Carfilzomib is currently being evaluated in 2 ongoing Phase 1 studies (CFZ001 [Renal] and CFZ002 [Hepatic]), 5 ongoing Phase 1b/2 studies (PX-171-007, PX-171-010, 2012-002 [CHAMPION 1], 2012-003 [CHAMPION 2], and CFZ004 [small cell lung cancer]), 4 ongoing Phase 3 studies (PX-171-009 [ASPIRE], PX-171-011 [FOCUS], 2011-003 [ENDEAVOR], and 2012-005 [CLARION]), and 2 ongoing Phase 1/2 studies sponsored by Ono Pharmaceutical Co, Ltd in Japan (ONO-7057-01 and ONO-7057-02).

Data are available from the following 10 company-sponsored Phase 1,1b, and 2 studies: PX-171-001, PX-171-002, PX-171-003, PX-171-004, PX-171-005, PX-171-006, PX-171-007, PX-171-008, PX-171-010 (ongoing), and 2012-002, (CHAMPION 1, ongoing). Of these, 9 studies enrolled multiple myeloma subjects. Study PX-171-007 also enrolled subjects with lymphoma and solid tumors. Study PX-171-008 enrolled solid tumor subjects only. Data also are available from a company-sponsored, Phase 2, expanded-access study (Study 2011-002 [C-MAP]) and 2 ongoing Phase 1/2 Ono-sponsored studies (ONO-7057-01 and ONO-7057-02). Furthermore, after the IB data cutoff date of 10 July 2014, a pre-planned interim analysis was performed for the Phase 3 Study PX-171-009 (ASPIRE) on 01 August 2014 and a final analysis was performed for the Phase 3 Study PX-171-011 (FOCUS) on 11 August 2014.

Five Phase 3 studies have been or are being conducted. Safety and efficacy results are available for 2 completed studies, Study PX-171-009 (ASPIRE) and Study PX-171-011 (FOCUS); subjects are still being followed for safety in both studies and for final OS in Study PX-171-009

(ASPIRE). Summaries for 3 ongoing studies, Study 2011-003 (ENDEAVOR), Study 2012-005 (CLARION), and Study CFZ014 (A.R.R.O.W.)

4.3.2 Antibody titer

Low titer = MFI < 2000 units at 1:4 dilution

High titer = MFI > 8000 units at 1:16 dilution

4.3.3 Functional DSA phenotypes

Complement fixing DSA = MFI > 500 units in neat serum by Luminex-C1q

Non-complement fixing DSA = MFI < 500 units in neat serum by Luminex-C1q

4.3.4 Kinetic DSA phenotypes

Early DSA = present within 6 months post-transplant

Late DSA = present after 6 months post-transplant

4.3.5 Immunologic DSA phenotypes

Memory response = sensitized pre-transplant with DSA pattern (MFI < 1000 units) de novo response = not sensitized with no detectable pre-transplant DSA pattern

- 4.3.6 Antibody-mediated rejection (AMR) diagnosis (must have first 2 criteria)
 - 1. Presence of DSA
 - 2. Allograft dysfunction (absence of another identifiable cause, except cellular rejection (ACR))

Fall of > 10% in FEV1, or

Fall of > 30% in FEF 25/75, or

New onset hypoxia/hypoxemia requiring supplemental oxygen, or

Need for mechanical ventilation

3. With or without pathologic findings consistent with AMR

Capillaritis

Endothelialitis

C4d pericapillary deposition in > 50% of biopsy

4.3.7 AMR phenotypes

Probable AMR alone = DSA, allograft dysfunction, no AMR pathologic findings, ACR grade ≤ A1

Definite AMR alone = DSA, allograft dysfunction, AMR pathologic findings, ACR grade ≤ A1

Mixed rejection = DSA, allograft dysfunction, with or without AMR pathologic findings, ACR grade ≥ A2

4.3.8 Bronchiolitis obliterans syndrome (BOS) diagnosis²⁴

Baseline FEV1 defined as mean of 2 best FEV1 post-transplant

BOS 0 = FEV1 > 80% of baseline

BOS 0p = FEV1 81-90% of baseline and/or FEF25/75 ≤ 75% of baseline

BOS 1 = FEV1 66-80% of baseline BOS 2 = FEV1 51-65% of baseline BOS 3 = FEV1 \leq 50% of baseline

4.3.9 Hypogammaglobulinemia, total serum IgG < 700 mg/dL

4.4 Study Endpoints

4.4.1 Primary endpoint

The primary endpoint of this study is the absolute change in DSA strength, titer, and complement fixation from day 1 to day 42. DSA strength will be determined by Luminex single-antigen bead testing in the neat serum and quantitated in units of mean fluorescent intensity. DSA titer will be determined by Luminex single-antigen bead testing in the diluted serum to 1:16 and quantitated in units of mean fluorescent intensity. DSA complement fixation will be determined by C1q-based Luminex single-antigen bead testing in the neat serum and quantitated in units of mean fluorescent intensity.

A 1:1 retrospective control group including lung transplant recipients from the University of Pittsburgh with Antibody Mediated Rejection will be created to describe differences in the endpoints using the CFZ-based regimen vs. historic standard of care.

4.4.2 Secondary endpoints

Secondary endpoints of this study include the following:

- 4.4.2.1 Absolute change in DSA strength, titer, and complement fixation from day 1 to day 90 and from day 42 to day 90. DSA strength will be determined by Luminex single-antigen bead testing in the neat serum and quantitated in units of mean fluorescent intensity. DSA titer will be determined by Luminex single-antigen bead testing in the diluted serum to 1:16 and quantitated in units of mean fluorescent intensity. DSA complement fixation will be determined by C1q-based Luminex single-antigen bead testing in the neat serum and quantitated in units of mean fluorescent intensity.
- 4.4.2.2 Absolute change in forced expiratory volume in 1 second (FEV1) from day 1 to day 42 and to day 90. FEV1 will be quantitated via UPMC PFT lab standard methods on routine pulmonary function testing obtained in the routine clinical care of these patients.
- 4.4.2.3 Presence or absence of pathologic changes consistent with AMR on transbronchial biopsy from day 1 to day 42. Pathologic changes consistent with AMR will be defined as follows: Complement-4d fixation on >50% (diffuse) of the capillaries in the biopsy by standard immunoperoxidase method, capillaritis by standard hematoxylin and eosin (H&E) stain; or endothelialitis by standard H&E stain.
- 4.4.2.4 Patient death at any time after day 1 attributable to AMR.
- A 1:1 retrospective control group including lung transplant recipients from the University of Pittsburgh with Antibody Mediated Rejection will be created to describe differences in the endpoints using the CFZ-based regimen vs. historic standard of care.

4.4.3 Safety outcomes

Safety outcomes of the study include the following:

- 4.4.3.1 Non-lung irreversible end-organ failure (e.g., end-stage renal disease) any time after day 1 attributable to carfilzomib.
- 4.4.3.2 Incidence of adverse effects (AE) requiring dose-modification (see section 5.3.1.2) any time during days 1-16.
- 4.4.3.3 Incidence of any AE at any time after day 1 as graded by the NIH Common Terminology Criteria for Adverse Events (CTCAE) (appendix B) criteria, as follows:
 - Grade 1: Mild; asymptomatic or mild symptoms; clinical or diagnostic observations only; intervention not indicated.
 - Grade 2: Moderate; minimal, local or noninvasive intervention indicated; limiting ageappropriate instrumental ADL (Instrumental ADL refer to preparing meals, shopping for groceries or clothes, using the telephone, managing money, etc.).
 - Grade 3: Severe or medically significant but not immediately life-threatening; hospitalization or prolongation of hospitalization indicated; disabling; limiting self-care ADL (self-care ADL refer to bathing, dressing and undressing, feeding self, using the toilet, taking medications, and not bedridden).
 - Grade 4: Life-threatening consequences; urgent intervention indicated.

Grade 5: Death related to AE.

- 4.4.3.4 Incidence of hypogammaglobulinemia any time after day 1.
- 4.4.3.5 Incidence of culture-proven *de novo* infection any time after day 1.
- 4.4.3.6 Diagnosis of systemic inflammatory response syndrome (SIRS) any time during days 1-16; requiring at least 2 of the following 4 criteria:

Body temperature: < 36 or > 38 degrees Celsius

Tachycardia: > 90 beats per minute

Tachypnea: > 20 breaths per minute

White blood cells: < 4000 or > 12000 cells/mm³

- 4.4.3.7 Patient death at any time after day 1 attributable to carfilzomib.
- A 1:1 retrospective control group including lung transplant recipients from the University of Pittsburgh with Antibody Mediated Rejection will be created to describe differences in the endpoints using the CFZ-based regimen vs. historic standard of care.

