5.1.2 Inclusion criteria

Adult lung transplant recipients ≥ 18 years of age who meet the diagnostic criteria for AMR as described in 4.3.6 who have underwent PFT testing unless intubated and transbronchial biopsy prior to enrollment. Patients who have not experienced improvement or regression are candidates for a second cycle of therapy on the protocol.

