5.1.3.2 Exclusion related to general health

Leukopenia defined as WBC < 2000 Neutropenia defined as ANC < 1000 Thrombocytopenia defined as platelets < 75000 x 10⁶ Known Child-Pugh B/C cirrhosis Total bilirubin > 4 ALT > 90 Known systolic heart failure with LVEF < 40%

Known pulmonary hypertension

Any uncontrolled comorbid condition

Pregnant women (negative serum pregnancy test required within 7 days prior to study drug administration for women of childbearing potential)

Breastfeeding women

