5.14 Data quality assurance

The Pulmonary Research Core will be responsible for data management of this trial, including quality checking of the data. Data will be collected and aggregated in REDCap. Investigators and support personnel from the research core will be responsible for entering the needed data into REDCap. In the event of discrepant data, clarification will be performed by the primary investigators.

6 Assessment of safety

Safety assessments will consist of monitoring and recording adverse events (AE) and serious adverse events (SAE) as defined in this section; measurement of protocol-specified hematology and basic chemistry laboratory values, measurement of protocol-specified vital signs, and other non-protocol specific tests that are deemed critical to the safety evaluation of the patient.

Investigators are responsible for reporting any SAE to Amgen as described below. Amgen will be responsible for reporting SAEs to the appropriate regulatory body.

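### The SIRS safety outcome has no baseline or new-onset rule and its window includes pre-dose day 1, so SIRS present before the first infusion counts as an on-study event

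*Combined protocol and SAP*

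**What the plan says.** Section 4.4.3.6 lists the outcome as "Diagnosis of systemic inflammatory response syndrome (SIRS) any time during days 1-16; requiring at least 2 of the following 4 criteria". The four criteria are temperature below 36 or above 38 degrees, pulse above 90, "Tachypnea: > 20 breaths per minute", and "White blood cells: < 4000 or > 12000 cells/mm³". The synopsis gives the same window.

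Section 5.6 says that assessments due on a dosing day come before the infusion unless otherwise noted. Appendix A schedules a history and physical and a blood count on day 1, then progress notes and blood counts on each of days 2 to 16.

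On entry:
- Section 5.1.3.2 excludes "Leukopenia defined as WBC < 2000" and sets no upper limit for white cells.
- The allograft-dysfunction part of the AMR diagnosis (section 4.3.6) can be met by "New onset hypoxia/hypoxemia requiring supplemental oxygen, or" "Need for mechanical ventilation".
- Section 5.1.2 takes patients "who have underwent PFT testing unless intubated", so intubated patients can enroll.
- Section 5.1.3.3 excludes life-threatening infection, active CMV disease and active varicella zoster, but not other infections.

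On data, section 6 promises "measurement of protocol-specified vital signs". Appendix B has daily white cell counts but no field for temperature, pulse, respiratory rate or SIRS itself.

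**The concern.** A safety outcome in a drug trial should tell the reader what happened after the drug was given. This one takes in findings made before the first dose, and nothing in its definition removes them.

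The neighbouring outcomes in section 4.4.3 show that the gap is particular to SIRS. Organ failure and death are limited to the time after day 1 and to events attributed to the drug. Infection must be de novo and after day 1. Hypogammaglobulinemia and general adverse events are limited to after day 1. Adverse events requiring dose modification share the days 1-16 window, but section 5.3.1.2 ties them to drug-related toxicity. SIRS has no onset term, no attribution term, and a window that opens on day 1.

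At stake is how the SIRS rate can be read. Section 4.4.3 also says that a retrospective control group will be used to describe differences in the endpoints. If the two groups differ in how ill patients were at the start, that difference would appear in the SIRS comparison, and no planned baseline status would allow it to be separated out.

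**Working it through.** **1. The plan's own figure.** The documents give no SIRS rate, power or alpha. The one design figure is the sample size (section 5.13.3): 10 per year × 3 years = 30. It reproduces and serves below only as the denominator.

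**2. What each entry state scores by definition** (two of four criteria needed):

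| State at entry | Criteria met by definition |
|---|---|
| Hypoxia needing oxygen | 0 |
| Mechanical ventilation | 0 |
| WBC 2000-3999 | 1 |

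None of these is SIRS on its own. A patient with one criterion at entry has SIRS before dosing if at least one of the other three is also present. If each is present independently with probability p (assumed), that chance is 1 − (1 − p)³:
- p = 5%: 1 − 0.95³ = 14%
- p = 10%: 1 − 0.90³ = 27%
- p = 20%: 1 − 0.80³ = 49%
- p = 30%: 1 − 0.70³ = 66%

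**3. What the counting rule does with SIRS present before dosing.** Let b be the proportion with SIRS before the first dose and q the new-onset rate among the rest. The documents give neither; both are assumptions.

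Crude count = 30b + 30(1 − b)q. New-onset count = 30(1 − b)q, out of 30(1 − b) patients. With q = 30%:

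| b | Pre-existing, 30b | New onset | Crude count | Crude rate | New-onset rate |
|---|---|---|---|---|---|
| 10% | 3 | 8.1 | 11.1 | 11.1/30 = 37% | 8.1/27 = 30% |
| 20% | 6 | 7.2 | 13.2 | 13.2/30 = 44% | 7.2/24 = 30% |
| 30% | 9 | 6.3 | 15.3 | 15.3/30 = 51% | 6.3/21 = 30% |

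The crude rate rises with illness at entry while the on-treatment rate stays fixed.

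**4. Share of events that is pre-existing.** Share = b / (b + (1 − b)q).
- Low end, b = 5%, q = 70%: 0.05 / (0.05 + 0.665) = 7%.
- High end, b = 50%, q = 10%: 0.50 / (0.50 + 0.05) = 91%.

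The share passes one half only when b exceeds q/(1 + q): 9% at q = 10%, 17% at q = 20%, 23% at q = 30%, 33% at q = 50%, 41% at q = 70%. The documents do not say on which side of that line the trial lies.

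**5. Whether other text closes the gap.**
- Section 5.13 plans to assess change from baseline in safety outcomes. It defines no baseline SIRS status and gives no rule for a yes/no outcome.
- Section 6.3.5 records a pre-existing condition only if it worsens. That governs the AE and SAE forms, not the outcome in 4.4.3.6.
- Baseline white cell count is collected in Appendix B. The other three components have no named field, so status before dosing could not be built from the planned data set.

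**The case against.** The strongest reply is that the plan already has pieces of a baseline. Section 5.13 names change from baseline, day-1 assessments precede infusion, the adverse-event definition covers events not previously seen in the patient, and section 6.2.3 requires a causality judgement. Two criteria at the same assessment is also the natural reading of a diagnosis. Patients are inpatients for at least 16 days, so vital signs should be in the notes. And this is one of seven safety outcomes in a 30-patient pilot, with no power calculation or numerical stopping limit resting on it.

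Much of this is fair and keeps the point small. But none of it is a rule for this outcome: the adverse-event provisions govern adverse-event recording, and the change-from-baseline sentence cannot be applied to SIRS without a definition that the plan lacks. Measuring before infusion makes the problem concrete, because it places a drug-free finding inside the window.

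Two stronger readings are tempting and should be resisted.
- A reader might infer that patients entering hypoxic, ventilated or with low white cells already have SIRS. They do not by definition: the first two states are not criteria, and the third supplies one of two.
- A reader might treat a patient with one criterion at entry who gains a second during the 16 days as pre-existing SIRS. That patient did not have SIRS at entry and would rightly still count under a new-onset rule. The chance of such an event describes background illness in an uncontrolled arm, not a missing baseline.

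**Conclusion.** The point holds in this form: as written, the outcome counts SIRS found before the first infusion as an on-study event, and entry criteria admit patients who may already carry one or more components. This follows from the text and needs no assumed rate.

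The size is not determinable from the documents. With assumed entry prevalence of 10%, 20% or 30%, 3, 6 or 9 of 30 patients would be counted before any drug. Over the wider assumed range (b 5-50%, q 10-70%) the pre-existing share of events runs from 7% to 91%. A reader might infer that most counted events would be pre-existing illness; that is neither shown nor excluded. The protocol's table of earlier carfilzomib experience (section 6.1.4) lists pyrexia at 28.2% and leukopenia at 10.2%, so some SIRS could arise on treatment.

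The point is minor: it affects how one safety rate is read, not the primary endpoint or the conduct of the trial.

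**What to change.** Rewrite 4.4.3.6 so that SIRS counts when at least two criteria are met at the same assessment after the first infusion, in patients with fewer than two criteria before dosing on day 1. Report the prevalence of SIRS before dosing on day 1 separately. Add temperature, pulse and respiratory rate to Appendix B, taken from the day-1 history and physical and the daily inpatient notes already in Appendix A; white cell count is there already.

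The cost is a short change of definition and three abstracted fields. No visit, test, eligibility rule or treatment changes. Patients with SIRS before dosing leave the new-onset denominator, so the estimate rests on somewhat fewer patients (24 instead of 30 if b were 20%). The change separates new from pre-existing SIRS; it does not show that the drug caused the new cases, which a single arm cannot do.
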